## Table 14.3.5.2.2 AIMS Total Score Results and Change from Baseline by Visit

#### Safety Analysis Set

This table will be similar to 14.3.5.1. Footnotes will be: Note: AIMS = Abnormal Movement Scale, Note: The AIMS total score is the sum of the scores for all 7 items and ranges between 0 and 28. If one or more items are missing at a visit the AIMS total score is missing. Note: Baseline is defined as the last non-missing measurement taken prior to first dose of double-blind study medication.

## Table 14.3.5.3.1 BARS Global Score Results and Change from Baseline by Visit

## Safety Analysis Set

This table will be similar to 14.3.5.1. Footnotes will be: Note: BARS = Barnes Akathisia Rating Scale, Note: The BARS Global Score is defined as the global clinical assessment of akathisia and assesses extrapyramidal symptoms on a 6point scale, whith 0 representing absence of symptoms and 5 representing severe akathesia. Note: Baseline is defined as the last non-missing measurement taken prior to first dose of double-blind study medication.

## Table 14.3.5.3.2 BARS Total Score Results and Change from Baseline by Visit

### Safety Analysis Set

This table will be similar to 14.3.5.1. Footnotes will be: Note: BARS = Barnes Akathisia Rating Scale, Note: The BARS total score is the sum of the scores for the first 3 items and ranges between 0 and 9. If one or more items are missing at a visit the BARS total score is missing. Note: Baseline is defined as the last non-missing measurement taken prior to first dose of double-blind study medication.

Author: [name]

Version Number: Version Date: Draft 2 09Jan2017 Page **101** of **144** 

Page 1 of x

Noven Pharmaceuticals, Inc. STATISTICAL ANALYSIS PLAN: PROTOCOL HP-3070-GL-04

Noven Pharmaceuticals, Inc. Protocol HP-3070-GL-04

Visit/ Assessment	Statistic	HP-3070 18.0 mg (N=xxx)	HP-3070 9.0 mg (N=xxx)	Placebo (N=xxx)
Baseline	N	XX	XX	XX
Subjects reporting at least one occurrence of suicidal	n (%)	xx (xx.x)	xx (xx.x)	xx (xx.x)
ideation or behavior				
Subjects reporting any type of suicidal behavior	n (%)	xx (xx.x)	xx (xx.x)	xx (xx.x)
Subjects reporting any type of sucicidal ideation	n (%)	xx (xx.x)	xx (xx.x)	xx (xx.x)
Week 1	Ν	XX	xx	xx
Subjects reporting at least one occurrence of suicidal	n (%)	xx (xx.x)	xx (xx.x)	xx (xx.x)
ideation or behavior				
Subjects reporting any type of suicidal behavior	n (%)	xx (xx.x)	xx (xx.x)	xx (xx.x)
Subjects reporting any type of sucicidal ideation	n (%)	xx (xx.x)	xx (xx.x)	xx (xx.x)

# Table 14.3.5.4.1 C-SSRS Suicidal Ideation by Visit Safety Analysis Set

Note: C-SSRS = Columbia-Suicide Severity Rating Scale.

Note: Any Suicidal Ideation is defined as any score greater than 0.

Note: Baseline is defined as the last non-missing measurement taken prior to first dose of double-blind study medication. Note: Percentages are calculated as  $(n/N) \times 100$ , where N is the number of subjects with data at the given visit.

Noven\HP-3070\XWA17541\Biostatistics\Production\Tables\xxxxx.sas ddmmmyyyy hh:mm Programming note: Repeat for all visits.

Author:

[name]

Version Number:

Version Date:

Draft 2 09Jan2017 Page **102** of **144** 

Noven Pharmaceuticals, Inc. STATISTICAL ANALYSIS PLAN: PROTOCOL HP-3070-GL-04

Noven Pharmaceuticals, Inc. Protocol HP-3070-GL-04 Page 1 of x

## Table 14.3.5.4.2 C-SSRS Most Severe Suicidal Ideation and Suicidal Behavior Safety Analysis Set

	HP-3070 18.0 mg (N=xxx) n (%)	HP-3070 9.0 mg (N=xxx) n (%)	Placebo (N=xxx) n (%)
Any Suicidal Ideation During Screening/Baseline	xx (xx.x)	xx (xx.x)	XX (XX.X)
1: Wish to be Dead	xx (xx.x)	xx (xx.x)	xx (xx.x)
2: Non-Specific Active Suicidal Thoughts	xx (xx.x)	xx (xx.x)	xx (xx.x)
3: Active Suicidal Ideation with Any Methods (Not Plan) without Intent to Act	xx (xx.x)	xx (xx.x)	xx (xx.x)
4: Active Suicidal Ideation with Some Intent to Act, without Specific Plan	xx (xx.x)	xx (xx.x)	xx (xx.x)
5: Active Suicidal Ideation with Specific Plan and Intent	xx (xx.x)	xx (xx.x)	xx (xx.x)
Any Suicidal Behavior During Screening/Baseline	xx (xx.x)	xx (xx.x)	xx (xx.x)
Actual Attempt	xx (xx.x)	xx (xx.x)	xx (xx.x)
Interrupted Attempt	xx (xx.x)	xx (xx.x)	xx (xx.x)
Aborted Attempt	xx (xx.x)	xx (xx.x)	xx (xx.x)
Preparatory Acts or Behavior	xx (xx.x)	xx (xx.x)	xx (xx.x)
Completed Suicide During Screening/Baseline	xx (xx.x)	xx (xx.x)	xx (xx.x)
Any Ideation or Behavior Suicidality During Screening/Baseline	xx (xx.x)	xx (xx.x)	xx (xx.x)
Both Ideation and Behavior Suicidality During Screening/Baseline	xx (xx.x)	xx (xx.x)	xx (xx.x)

Note: C-SSRS = Columbia-Suicide Severity Rating Scale.

Note: Any Suicidal Ideation is defined as any score greater than 0.

Note: Treatment-emergent suicidal ideation is defined as no suicidal ideation at baseline/screening and any suicidal ideation postbaseline.

Note: Worsening suicidal ideation is defined as most severe suicidal ideation post-baseline more severe than at baseline/screening.

Note: Baseline is defined as the last non-missing measurement taken prior to first dose of double-blind study medication.

Note: Percentages are calculated as (n/N)\*100.

Note: Subjects are counted only at their most severe suicidal ideation type and at their most severe behavior type.

Noven/HP-3070/XWA17541/Biostatistics/Production/Tables/xxxxx.sas ddmmmyyyy hh:mm

Author: A

[name]

Version Number:

Version Date:

Draft 2 09Jan2017 Page **103** of **144** 

Noven Pharmaceuticals, Inc. STATISTICAL ANALYSIS PLAN: PROTOCOL HP-3070-GL-04

Noven Pharmaceuticals, Inc. Protocol HP-3070-GL-04 Page 2 of x

# Table 14.3.5.4.2 C-SSRS Most Severe Suicidal Ideation and Suicidal Behavior Safety Analysis Set

	HP-3070 18.0 mg	HP-3070 9.0 mg	Placebo
	(N=xxx)	(N=XXX)	(N=xxx)
	n (%)	n (%)	n (%)
Any Suicidal Ideation During Double-Blind Treatment Period	xx (xx.x)	xx (xx.x)	xx (xx.x)
1: Wish to be Dead	xx (xx.x)	xx (xx.x)	xx (xx.x)
2: Non-Specific Active Suicidal Thoughts	xx (xx.x)	xx (xx.x)	xx (xx.x)
3: Active Suicidal Ideation with Any Methods (Not Plan) without Intent to Act	xx (xx.x)	xx (xx.x)	xx (xx.x)
4: Active Suicidal Ideation with Some Intent to Act, without Specific Plan	xx (xx.x)	xx (xx.x)	xx (xx.x)
5: Active Suicidal Ideation with Specific Plan and Intent	xx (xx.x)	xx (xx.x)	xx (xx.x)
Any Suicidal Behavior During Double-Blind Treatment Period	xx (xx.x)	xx (xx.x)	xx (xx.x)
Actual Attempt	xx (xx.x)	xx (xx.x)	xx (xx.x)
Interrupted Attempt	xx (xx.x)	xx (xx.x)	xx (xx.x)
Aborted Attempt	xx (xx.x)	xx (xx.x)	xx (xx.x)
Preparatory Acts or Behavior	xx (xx.x)	xx (xx.x)	xx (xx.x)
Completed Suicide During Double-Blind Treatment Period	XX (XX.X)	xx (xx.x)	xx (xx.x)
Any Ideation or Behavior Suicidality During Double-Blind Treatment Period	xx (xx.x)	xx (xx.x)	xx (xx.x)
Without Ideation or Behavior Suicidality During Screening/Baseline	xx (xx.x)	xx (xx.x)	xx (xx.x)
Both Ideation and Behavior Suicidality During Double-Blind Treatment Period	xx (xx.x)	xx (xx.x)	xx (xx.x)
Without Ideation and Behavior Suicidality During Screening/Baseline	xx (xx.x)	xx (xx.x)	xx (xx.x)

Note: C-SSRS = Columbia-Suicide Severity Rating Scale.

Note: Any Suicidal Ideation is defined as any score greater than 0.

Note: Treatment-emergent suicidal ideation is defined as no suicidal ideation at baseline/screening and any suicidal ideation postbaseline.

Note: Worsening suicidal ideation is defined as most severe suicidal ideation post-baseline more severe than at baseline/screening. Note: Baseline is defined as the last non-missing measurement taken prior to first dose of double-blind study medication.

Note: Percentages are calculated as (n/N)\*100.

Note: Subjects are counted only at their most severe suicidal ideation type and at their most severe behavior type.

Noven\HP-3070\XWA17541\Biostatistics\Production\Tables\xxxxx.sas ddmmmyyyy hh:mm

Author:	[name]	Version Number:	Draft 2
		Version Date:	09Jan2017
			Page 104 of 144

Noven Pharmaceuticals, Inc. Protocol HP-3070-GL-04 Page 1 of x

Table 14.3.6 Summary of Patch Adhesion,	, Adhesive Residue, and Skin Irritation
Safety Ana	lysis Set

Visit/ Assessment	Statistic	HP-3070 18.0 mg	HP-3070 9.0 mg	Placebo
Over the Entire Double-Blind Treatment Period	N	XX	xx	XX
Any Complete Detachment	n (%)	xx (xx.x)	xx (xx.x)	xx (xx.x)
Any Partial Detachment	n (%)	xx (xx.x)	xx (xx.x)	xx (xx.x)
Adhesive Residue				
0=None	n (%)	xx (xx.x)	xx (xx.x)	xx (xx.x)
1=Mild	n (%)	xx (xx.x)	xx (xx.x)	xx (xx.x)
2=Medium	n (%)	xx (xx.x)	xx (xx.x)	xx (xx.x)
3=Heavy	n (%)	xx (xx.x)	xx (xx.x)	xx (xx.x)
Any Occurrence of Medium or Heavy	n (%)	xx (xx.x)	xx (xx.x)	xx (xx.x)
Week 1	Ν	xx	xx	xx
Any Complete Detachment	n (%)	xx (xx.x)	xx (xx.x)	xx (xx.x)
Any Partial Detachment	n (%)	xx (xx.x)	xx (xx.x)	xx (xx.x)

Note: N = number of subjects with data at the given visit.

Note: A subject's maximum adhesive residue score and maximum skin irritation score per visit are shown.

Note: Percentages are calculated as (n/N) \* 100.

Note: Patch adhesion is determined from the following yes/no questions: "Is the patch fully attached to the skin?" and "If 'No', did the patch detach completely?"

Note: Skin irritation combined score is the sum of the numerical scores from the skin irritation - dermal response score and the skin irritation - other effects scores, where N=0, A=0, B=1, C=2, F=3, G=3 and H=3 for the other effects score. If no grade was assigned for the other effects observations (N) score the combined score will consist of the dermal response scale score only.

Note: Skin irritation concatenated score is determined by concatenating the dermal response score and other effects score (i.e., ON, 1N, 2N, 2A, 2B, 3N, 3A, 3B, 3C, 3F, etc.).

Noven/HP-3070/XWA17541/Biostatistics/Production/Tables/xxxxx.sas ddmmmyyyy hh:mm

Author: [name]

 Version Number:
 Draft 2

 Version Date:
 09Jan2017

 Page 105 of 144

Noven Pharmaceuticals, Inc. Protocol HP-3070-GL-04 Page 2 of x

## Table 14.3.6 Summary of Patch Adhesion, Adhesive Residue, and Skin Irritation Safety Analysis Set

Visit/ Assessment	Statistic	HP-3070 18.0 mg	HP-3070 9.0 mg	Placebo
		2	2	
Adhesive Residue				
0=None	n (%)	xx (xx.x)	xx (xx.x)	xx (xx.x)
1=Mild	n (%)	xx (xx.x)	xx (xx.x)	xx (xx.x)
2=Medium	n (%)	xx (xx.x)	xx (xx.x)	xx (xx.x)
3=Heavy	n (%)	xx (xx.x)	xx (xx.x)	xx (xx.x)
Any Occurrence of Medium or Heavy	n (%)	xx (xx.x)	xx (xx.x)	xx (xx.x)
Skin Irritation - Dermal Response Scale				
0=No evidence of irritation	n (%)	xx (xx.x)	xx (xx.x)	xx (xx.x)
1=Minimal erythema	n (%)	xx (xx.x)	xx (xx.x)	xx (xx.x)
2=Definite erythema, readily visible; minimal edema or minimal papular response	n (%)	xx (xx.x)	xx (xx.x)	xx (xx.x)
3=Erythema and papules	n (%)	xx (xx.x)	xx (xx.x)	xx (xx.x)
4=Definite edema	n (%)	xx (xx.x)	xx (xx.x)	xx (xx.x)
5=Erythema, edema, and papules	n (%)	xx (xx.x)	xx (xx.x)	xx (xx.x)
6=Vesicular eruption	n (%)	xx (xx.x)	xx (xx.x)	xx (xx.x)
7=Strong reaction spreading beyond test (application) site	n (%)	xx (xx.x)	xx (xx.x)	xx (xx.x)

Note: N = number of subjects with data at the given visit.

Note: A subject's maximum adhesive residue score and maximum skin irritation score per visit are shown.

Note: Percentages are calculated as (n/N)\*100.

[name]

Author:

Note: Patch adhesion is determined from the following yes/no questions: "Is the patch fully attached to the skin?" and "If 'No', did the patch detach completely?"

Note: Skin irritation combined score is the sum of the numerical scores from the skin irritation - dermal response score and the skin irritation - other effects scores, where N=0, A=0, B=1, C=2, F=3, G=3 and H=3 for the other effects score. If no grade was assigned for the other effects observations (N) score the combined score will consist of the dermal response scale score only.

Note: Skin irritation concatenated score is determined by concatenating the dermal response score and other effects score (i.e., ON, 1N, 2N, 2A, 2B, 3N, 3A, 3B, 3C, 3F, etc.).

Noven\HP-3070\XWA17541\Biostatistics\Production\Tables\xxxxx.sas ddmmmyyyy hh:mm

Version Number:	Draft 2
Version Date:	09Jan2017
	Page 106 of 144

Noven Pharmaceuticals, Inc. Protocol HP-3070-GL-04 Page 3 of x

## Table 14.3.6 Summary of Patch Adhesion, Adhesive Residue, and Skin Irritation Safety Analysis Set

Visit/ Assessment	Statistic	HP-3070 18.0 mg	HP-3070 9.0 mg	Placebo
Skin Irritation - Other Effects				
A(0)=Slightly glazed appearance	n (%)	xx (xx.x)	xx (xx.x)	xx (xx.x)
B(1)=Marked glazing	n (%)	xx (xx.x)	xx (xx.x)	xx (xx.x)
C(2)=Glazing with peeling and cracking	n (%)	xx (xx.x)	xx (xx.x)	xx (xx.x)
F(3)=Glazing with Fissures	n (%)	xx (xx.x)	xx (xx.x)	xx (xx.x)
G(3)=Film of dried, serous exudate covering all or part of the	n (%)	xx (xx.x)	xx (xx.x)	xx (xx.x)
patch site				
H(3)=Small petechial erosions and/or scabs	n (%)	xx (xx.x)	xx (xx.x)	xx (xx.x)
Skin Irritation - Combined Score (Concatenated Score)				
0=No evidence of irritation / No other effects (0N)	n (%)	xx (xx.x)	xx (xx.x)	xx (xx.x)
1=Minimal erythema, barely perceptible / No other effects (1N)	n (%)	xx (xx.x)	xx (xx.x)	xx (xx.x)
2=Definite erythema / No other effects (2N)	n (%)	xx (xx.x)	xx (xx.x)	xx (xx.x)
3=Erythema and papules / No other effects (3N)	n (%)	xx (xx.x)	xx (xx.x)	xx (xx.x)
	n (%)	xx (xx.x)	xx (xx.x)	xx (xx.x)
<repeat all="" and="" combinations="" dermal="" e<="" for="" of="" other="" response="" scale="" td="">effects>				</repeat>	effects>			

Note: N = number of subjects with data at the given visit.

Note: A subject's maximum adhesive residue score and maximum skin irritation score per visit are shown.

- Note: Percentages are calculated as (n/N) \* 100.
- Note: Patch adhesion is determined from the following yes/no questions: "Is the patch fully attached to the skin?" and "If 'No', did the patch detach completely?"
- Note: Skin irritation combined score is the sum of the numerical scores from the skin irritation dermal response score and the skin irritation other effects scores, where N=0, A=0, B=1, C=2, F=3, G=3 and H=3 for the other effects score. If no grade was assigned for the other effects observations (N) score the combined score will consist of the dermal response scale score only.
- Note: Skin irritation concatenated score is determined by concatenating the dermal response score and other effects score (i.e., ON, 1N, 2N, 2A, 2B, 3N, 3A, 3B, 3C, 3F, etc.).

Noven\HP-3070\XWA17541\Biostatistics\Production\Tables\xxxxx.sas ddmmmyyyy hh:mm Programming note: Repeat for all visits.

Author:	[name]	Version Number:	Draft 2
		Version Date:	09Jan2017
			Page 107 of 144

IMS Health & Quintiles are now

Noven Pharmaceuticals, Inc. Protocol HP-3070-GL-04 Page 1 of x

# Table 14.3.7 Summary of Plasma Asenapine and Desmethyl-asenapine Concentrations (ng/mL)) by TreatmentPK Analysis Set

Plasma Asenapine (no	g/mL) d mg			
Visit	Statistic	2 hours	14 Hours	22 Hours
Week 3/ Day 21	n	XX	XX	XX
noon o, bay bi	Mean	 xxxx.xx	 xxxx.xx	 xxxx.xx
	SD	xxxx.xx	xxxx.xx	xxxx.xx
	%CV	XXXX.XX	xxxx.xx	XXXX.XX
	Median	XXXX.XX	XXXX.XX	XXXX.XX
	Min	XXXX.XX	xxxx.xx	xxxx.xx
	Max	XXXX.XX	XXXX.XX	XXXX.XX
	Geometric Mean	****	xxxx.xx	****
Week 6/ Day 42	n	XX	xx	xx
-	Mean	XXXX.XX	XXXX.XX	XXXX.XX
	SD	XXXX.XX	xxxx.xx	xxxx.xx
	%CV	XXXX.XX	XXXX.XX	XXXX.XX
	Median	XXXX.XX	XXXX.XX	XXXX.XX
	Min	XXXX.XX	XXXX.XX	XXXX.XX
	Max	XXXX.XX	XXXX.XX	XXXX.XX
	Geometric Mean	xxxx.xx	XXXX.XX	XXXX.XX

Note: Concentrations that are  ${\rm BLQ}$  are treated as zero for descriptive statistics. Note: Summary statistics apply to Pharmacokinetic Population only

Noven\HP-3070\XWA17541\Biostatistics\Production\Tables\xxxxx.sas ddmmmyyyy hh:mm Programming note: Repeat for HP-3070 18 mg. Blood samples will be collected for asenapine and desmethyl-asenapine concentration; on Day 21 and 42 of HP-3070 9 mg and 18 mg at 2, 14 and 22 hours after dosing.

Author:

[name]

Version Number: Version Date:

Draft 2

09Jan2017 Page 108 of 144

Protocol No. HP-3070-GL-04 14 September 2018

Noven Pharmaceuticals, Inc. STATISTICAL ANALYSIS PLAN: PROTOCOL HP-3070-GL-04

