The study will evaluate 9.0mg (HP-3070 9.0 mg) and 18.0 mg (HP-3070 18.0 mg) of HP-3070 transdermal patches versus placebo transdermal patches. Patches will be applied by site personnel at approximately the same time daily and each patch will be worn for 24 hours. Every day, 24 hours (±15 minutes) after patch application, site personnel will remove previous day's patches and apply new patches.

All subjects will have a follow-up contact (site visit or telephone call, at the discretion of the Investigator) 30 days after the last patch is removed. This contact will be used to collect information about any Adverse Events (AEs) or Serious Adverse Events (SAEs) that may have occurred since discharge and to follow-up on any Adverse Events (AEs) that were on-going at discharge.

Assuming an effect size of 0.35 on the change in PANSS total score from baseline to Week 6 for the two pairwise comparisons between each active HP-3070 treatment arm and placebo, the power for detecting a statistically significant HP-3070 advantage will be approximately 0.90 having 204 evaluable subjects per each treatment arm, using a two-sided alpha level of 0.025 for each comparison. A two-sided overall type I error is equal to 0.05. Having three treatment arms, the total number of subjects randomized in the trial and included in primary analysis set will be approximately 612.

The effect size of 0.35 (difference between means equal to 7 and common standard deviation (SD) equal to 20) was chosen based on the lowest effect size observed in results from the studies conducted with sublingual (SL) asenapine and approved by the Food and Drug Administration (FDA) (Sycrest®/SAPHRIS® [Study 041004, and Study 041023]).

A sample size recalculation (SSR) will be conducted as described in Section 4.2 on the blinded data after approximately 50% of the originally planned number of subjects have been randomized and completed up to 6 weeks of study treatment.

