# 5.5. PHARMACOKINETIC ANALYSIS SET

The Pharmacokinetic Analysis Set (PAS) includes all subjects who have at least one dose of study medication during the double blind treatment period and have at least one blood sample for pharmacokinetic (PK) assessment. Subjects may be excluded from the PAS set if they significantly violate inclusion or exclusion criteria, significantly violate the protocol in a way that may influence the PK analysis, if any unexpected error occurs during the study that may influence the PK analysis (e.g., early detachment of transdermal systems, apparent sample switching, etc.) or if their data are unavailable or incomplete. The PAS will be used for the analysis with model based approach as well as for the presentation of descriptive summaries of PK data. Excluded cases will be documented together with the reason for exclusion.

Analysis dataset for pharmacokinetic assessments will be created by Metrum Research Group, LLC.

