## **16.3. LABORATORY EVALUATIONS**

A central laboratory designated by the Sponsor will be used for all laboratory assessments during the trial. If an immediate result is required, a sample should be sent to both the local and central laboratory.

Laboratory assessments will include standard measures of hematology, clinical chemistry [including prolactin levels], urinalysis, urine drug screen, and some additional tests as per protocol, Section 6.3. Pregnancy testing will be done for women of child-bearing capacity.

The central laboratory will not report prolactin levels to the sites, Sponsor, or other personnel involved in the study conduct until the overall study unblinding at final analysis, because this could potentially result in unblinding the treatment.

Urine drug screens may be done at the Investigator's discretion. If the subject is allowed to leave the hospital during study, an alcohol breathalyzer and urine drug tests must be done when the subject returns.

Summary tables will summarize laboratory data for each scheduled time point based on the visits at which samples were collected. Unscheduled evaluations will be presented in subject listings, but will not be summarized in tables. Unscheduled evaluations will be used in the determination of baseline values.

All available laboratory data will be presented in subject listings.

Presentations will use standard international (SI) Units for all laboratory tests.

Quantitative laboratory measurements reported as "< X", i.e. below the lower limit of quantification, or "> X", i.e. above the upper limit of quantification, will be converted to X for the purpose of quantitative summaries, but will be presented as originally recorded, i.e. as "< X" or "> X" in the subject listings.

Document:	\\quintiles.net\Enterprise\Apps\sas	data\SASb\SAS\Noven\HP-	
	3070\XWA17541\Biostatistics\Docu	umentation\SAP\Final 6\Noven HP-3070-GL-04 S	AP text Final
	6_18Jan2018.docx		
Author:	[name]	Version Number:	Final 6
		Version Date:	18Jan2018
Template No:	CS TP BS016 – Revision 3	Reference:	CS WI BS005

Effective Date: 01May2012

Copyright © 2012 Quintiles Transnational Corp. All rights reserved.

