# **17. PHARMACOKINETICS**

At least 3 blood samples will be collected at 2, 14, and 22 hours after application of the patch with  $\pm$  2 hourwindow on Day 21 and 42.

Individual plasma concentrations will be presented in subject listings and descriptive statistics for plasma concentration will also be summarized. Actual sampling time after doing will be used for the analysis.

A model-based approach will be used to assess the impact of covariates on asenapine exposure (population pharmacokinetics) and to explore the exposure-response relationship of relevant endpoints. These analysis will be done by Metrum Research Group LLC.

These analysis will be conducted using standard population nonlinear mixed effects modeling methods. Details for model based analysis (such as the choice of studies/data to be included for analysis, covariates to be tested, data handling, model development, model validation) is not covered by this statistical analysis plan and will be described in a stand-alone modeling and simulation plan prior to database lock.

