# Listing 16.2.3.9 Plasma Concentrations of Asenapine and Desmethyl-asenapine (ng/mL) by Treatment PK Analysis Set

Subject ID	Treatment	Visit	Scheduled Time (hr)	Sample Collection Date/Time	Actual Time (hr)	Asenapine Concentration (ng/mL)	Desmethyl- asenapine Concentration (ng/mL)	Comment
xxxx- xxxx	HP-3070 9.0 mg	Week 3	2	DDMONYYYY/HH:MM	х	xx.xx	xx.xx	
			14	DDMONYYYY/HH:MM	х	xx.xx	xx.xx	
			22	DDMONYYYY/HH:MM	х	xx.xx	xx.xx	
xxxx-	HP-3070	Week	2	DDMONYYYY/HH:MM	х	xx.xx	xx.xx	
XXXX	9.0 mg	6						
			14	DDMONYYYY/HH:MM	х	XX.XX	xx.xx	
			22	DDMONYYYY/HH:MM	х	xx.xx	xx.xx	
xxxx-	HP-3070	Week	2	DDMONYYYY/HH:MM	х	xx.xx	xx.xx	
XXXX	18.0 mg	3						
			14	DDMONYYYY/HH:MM	х	xx.xx	xx.xx	
			22	DDMONYYYY/HH:MM	х	xx.xx	xx.xx	
xxxx-	HP-3070	Week	2	DDMONYYYY/HH:MM	х	xx.xx	xx.xx	
XXXX	18.0 mg	6						
			14	DDMONYYYY/HH:MM	х	XX.XX	xx.xx	
			22	DDMONYYYY/HH:MM	х	XX.XX	xx.xx	

Note: The lower limit of quantification is 0.0200 ng/mL.

Note to Programmer: Sort by Subject No. and Treatment. Blood samples will be collected for PK analysis of asenapine and desmethylasenapine; on Day 21 and 42 for both treatments (9 and 18 mg) at 2, 14 and 22 hours after dosing.

Author:

[name]

Version Number:

Version Date:

Draft 2 09Jan2017 Page 144 of 144

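### Table 14.3.7 sets BLQ concentrations to zero for every descriptive statistic, which makes the geometric mean zero or undefined in any cell holding a BLQ sample

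*SAP*

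**What the plan says.** The shell for Table 14.3.7 lists n, mean, SD, %CV, median, minimum, maximum and "Geometric Mean" at 2, 14 and 22 hours, for Week 3/Day 21 and again for Week 6/Day 42. The programming note repeats the layout for the 18 mg dose and covers asenapine and desmethyl-asenapine. Placebo samples do not enter. The footnote states that BLQ concentrations "are treated as zero for descriptive statistics".

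Other parts of the SAP that bear on this:

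- Section 17 says that "descriptive statistics for plasma concentration will also be summarized" and gives no BLQ rule. The stand-alone modelling and simulation plan it mentions covers the model-based analysis, not this table.
- Section 5.5 defines the pharmacokinetic analysis set, used for the modelling "as well as for the presentation of descriptive summaries of PK data". A BLQ result is not a listed ground for exclusion.
- Section 16.3 has a below-limit rule, under which a result reported as less than X "will be converted to X for the purpose of quantitative summaries", but it governs safety laboratory data.
- Listing 16.2.3.9 notes: "The lower limit of quantification is 0.0200 ng/mL".

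**The concern.** The footnote is worded for all descriptive statistics in the table, and the geometric mean is one of them. Zero is a usable value for a mean, SD, median or minimum. It is not usable in a product or a logarithm. The rule therefore fails in exactly the cells where it applies.

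A programmer who meets such a cell has three outcomes open: print 0, print a missing value, or let the log of zero fall out of the calculation. The third contradicts the footnote. It also leaves a geometric mean based on fewer samples than the n shown above it, with the lowest values removed. The SAP does not say which of these is intended, so the choice would be made at programming. At stake is the usability of one exposure statistic in a descriptive table.

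**Working it through.** The SAP gives no figure to reproduce here. The check is algebraic, with a numerical illustration.

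**Inputs from the SAP.** BLQ = 0 for descriptive statistics and a geometric mean row (both Table 14.3.7); LLOQ 0.0200 ng/mL (Listing 16.2.3.9), so LLOQ/2 = 0.0100 ng/mL; a planned arm size from Section 3.1, "having 204 evaluable subjects per each treatment arm", taken as the number of samples per cell.

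**Assumed.** Lognormal concentrations with log-SD 0.5 and a geometric mean (GM) of 0.5, 2 or 4 ng/mL. The SAP gives no concentration levels.

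**Algebra.** GM = (x1 × x2 × … × xn)^(1/n) = exp[(1/n) Σ ln xi]. If any xi = 0, the product is 0 and ln(0) is undefined. This holds whatever the other values are.

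**Illustration, n = 204 (ng/mL).**

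| Assumed GM | BLQ samples | As written | Quantifiable only (n) | BLQ = LLOQ/2 | BLQ = LLOQ |
|---|---|---|---|---|---|
| 0.5 | 1 | 0 | 0.50 (203) | 0.49 | 0.49 |
| 0.5 | 5 | 0 | 0.50 (199) | 0.45 | 0.46 |
| 2 | 1 | 0 | 2.00 (203) | 1.95 | 1.96 |
| 2 | 5 | 0 | 2.00 (199) | 1.76 | 1.79 |
| 4 | 1 | 0 | 3.99 (203) | 3.87 | 3.89 |
| 4 | 5 | 0 | 4.03 (199) | 3.48 | 3.54 |

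The small departures of the quantifiable-only column from the assumed GM reflect which simulated values were replaced.

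In the row with GM 2 and one BLQ sample, the arithmetic mean moves only from 2.215 to 2.208. The zero rule does no material harm there.

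A hand check of the size of a substitution, with n = 200 and an assumed GM of 4: exp[ln(0.01/4)/200] = 0.970. One sample at LLOQ/2 lowers the geometric mean by about 3%; one sample at zero removes it.

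**How many cells could be affected.** Two doses × two days × three times = 12 cells per analyte, 24 for the two analytes. If each sample independently had BLQ probability p, the chance of at least one in a cell of 204 is 1 − (1 − p)^204:

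| Assumed p | Chance that a cell is affected |
|---|---|
| 0.1% | 18% |
| 0.5% | 64% |
| 1% | 87% |
| 2% | 98% |

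These values of p are a range, not an estimate.

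**The case against.** The strongest reply is that BLQ values should be rare in this table, and that part largely stands for asenapine. Subjects are hospitalised (Section 3.1) and staff apply the patches daily. Completely detached patches are replaced if at least 6 hours remain before the next dose (Section 13). Section 15.1.3 gives a mean half-life from the patch of 29.7 to 31.3 hours. Assuming simple exponential decline:

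- From 4 ng/mL (assumed) to 0.02 takes log2(200) = 7.6 half-lives, about 227 to 239 hours, or 9.5 to 10 days.
- From 0.5 ng/mL (assumed) it takes log2(25) = 4.6 half-lives, about 5.7 to 6.1 days.

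A reader might infer that a single detached or missed patch would produce BLQ results. These figures do not support that for the parent drug. For the metabolite, the SAP gives no levels from which to argue either way.

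Section 5.5 also allows exclusion for early detachment and apparent sample switching. That narrows the problem but does not close it: exclusion is discretionary and works at subject level.

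A reader might also infer that low values would vanish without trace. They would not. If the footnote is followed for the minimum, that row shows zero, and Listing 16.2.3.9 shows the individual concentrations with the LLOQ. A geometric mean of 0 beside a non-zero mean and median would be noticed. What would not show in the table is how many samples lie behind the geometric mean if the program drops zeros.

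None of this changes the algebra. The footnote exists for the case where a BLQ value occurs, and in that case it does not work.

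**Conclusion.** The rule is wrong as written for the geometric mean. In any cell of Table 14.3.7 with at least one BLQ sample, that statistic is 0 or undefined, or it is computed on fewer samples than the printed n, contrary to the footnote. This conclusion needs no assumption about the drug. The sizes do: at assumed geometric means of 0.5 to 4 ng/mL and one BLQ sample in 204, workable rules stay within about 3% of the assumed value, against 0 under the footnote.

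The point is minor. The BLQ frequency in the active arms on Days 21 and 42 is not given, so the number of cells affected is unknown and could be none. A reader might infer that the exposure-response conclusions or the efficacy results are compromised. The SAP does not support that: the table is descriptive, the model-based work has its own plan for data handling, and the primary and key secondary analyses do not use these concentrations.

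**What to change.** Reword the Table 14.3.7 footnote so that BLQ = 0 applies to the mean, SD, %CV, median, minimum and maximum only. Give the geometric mean its own rule, fixed before unblinding. Either of these would do:

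- quantifiable values only, with their n printed beside the geometric mean; or
- BLQ set to LLOQ/2 = 0.0100 ng/mL, with the footnote saying that this differs from the zero used for the other rows.

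Reporting the statistic as not calculated when a cell contains a BLQ value would also be acceptable. Which rule is chosen matters less than that one is stated.

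Add a row with the number and percentage of BLQ samples at each time point, so that a reader can judge the effect of the rule.

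The cost is one footnote and one row in the shell. No new data are needed and no other analysis changes.
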